9.10.14. Study Drug Administration

Patients should self-administer the assigned number of capsules orally once a day in the morning at the time points indicated in [Table 3](#) or [Table 4](#) and [Table 5](#) or [Table 6](#). On days when PK samples are collected, patients should not self-administer study drug. Study staff will administer study drug at the clinic following collection of the first PK sample.

A vomited dose should not be replaced. Missed doses may be taken in the afternoon or evening of the same day. A double dose (e.g., missed dose from previous day and dose for current day) should not be taken.

For patients enrolled in Cohorts 3 and 4, as well as patients enrolled in Part 2 of the study, dose de-escalation may occur any time after a DLT occurs.

9.10.15. Study Drug Dispensation and Collection

Study drug will be dispensed to the patient and collected from the patient at the time points indicated in [Table 3](#) or [Table 4](#) and [Table 5](#) or [Table 6](#). For patients enrolled in Cohorts 3 and 4, dose escalation may occur at Week 4.

9.10.16. Telephone Contact

Patients will be contacted by telephone at the time points indicated in [Table 3](#) or [Table 4](#) and [Table 5](#) or [Table 6](#). Patients will be asked about their body weight and other signs of fluid retention. If fluid retention is suspected, the patient should be brought into the clinic and evaluated by the Investigator as soon as possible, as detailed in Section [9.1.1](#).

9.10.17. Adverse Event Collection

Patients should be observed for general appearance, presence of illness or injury, or signs indicative of a concurrent illness at the time points indicated in [Table 3](#) or [Table 4](#) and [Table 5](#) or [Table 6](#). Patients should be instructed to volunteer any information regarding AEs at any time during the study, or query the patients with an open question regarding any AEs they may be experiencing (e.g., “How have you been feeling since your last visit?”). Any findings are to be documented. They may also be asked if they have been hospitalized, had any accidents, used any new medications, or changed concomitant medication regimens (including prescription drugs, over-the-counter medications, vitamins, herbal products, and minerals). Responses must be documented in the source documents.

9.10.18. Clinical Chemistry

Samples will be collected for the following clinical chemistry analyses at the time points indicated in [Table 3](#) or [Table 4](#) and [Table 5](#) or [Table 6](#): ferritin, creatine kinase (CK), blood urea nitrogen (BUN), creatinine enzymatic, total bilirubin, direct bilirubin, alanine aminotransferase (ALT), aspartate aminotransferase (AST), alkaline phosphatase, sodium, potassium, calcium, phosphorus, uric acid, total protein, glucose, albumin, lactate dehydrogenase (LDH), magnesium, chloride, bicarbonate, gamma-glutamyl transpeptidase (GGT). An eGFR using the MDRD formula ($eGFR = 175 \times \text{standardized serum creatinine}^{-1.154} \times \text{age}^{-0.203} \times 1.212$ [if black] $\times 0.742$ [if female]) will be calculated at the Screen A visit only for eligibility purposes. Women of child-bearing potential will require a serum pregnancy test (hCG-Qual) at Screen A or at any point in time if a pregnancy is suspected.

9.10.19. N-Terminal Pro-Brain Natriuretic Peptide and Brain Natriuretic Peptide

Samples will be collected for NT-Pro BNP and BNP at the time points indicated in [Table 3](#) or [Table 4](#) and [Table 5](#) or [Table 6](#). As BNP and NT-Pro BNP may be affected by recent exercise, patients must be allowed to rest for a minimum period of one-hour following arrival at the clinic and prior to obtaining this blood sample. Similarly, this sample must be taken prior to the 6MWT. This sample should be taken with the patient in the same position at all appropriate visits, e.g., sitting or semi-recumbent.

After the Week 32 study visit, only NT-Pro BNP should be collected at study visits, as shown in [Table 5](#) and [Table 6](#).

Detailed instructions on collection, storage and shipment of the sample will be provided in the central laboratory manual provided to the Investigator.

9.10.20. Hematology

Samples will be collected for the following hematology assessments at the time points indicated in [Table 3](#) or [Table 4](#) and [Table 5](#) or [Table 6](#): hematocrit, hemoglobin, red blood cell (RBC) count, white blood cell (WBC) count, neutrophils, bands (if detected), lymphocytes, monocytes, basophils (if detected), eosinophils (if detected), absolute platelet count, mean corpuscular hemoglobin (MCH), mean corpuscular volume (MCV), and mean corpuscular hemoglobin concentration (MCHC).

9.10.21. Urinalysis and Microscopy

Samples will be collected for the following urinalysis and microscopy assessments at the time points indicated in [Table 3](#) or [Table 4](#) and [Table 5](#) or [Table 6](#): specific gravity, ketones, pH, protein, blood, glucose, clarity, color, leukocytes, nitrite, bilirubin, and a microscopic examination (if indicated based on laboratory results).

9.10.22. Virus Serology

Blood samples will be collected for testing for hepatitis B and hepatitis C at the time point indicated in [Table 3](#) or [Table 4](#).

9.10.23. 6-Minute Walk Test

A 6-minute walk test (6MWT) will be administered to patients at the time points indicated [Table 3](#) or [Table 4](#) and [Table 5](#) or [Table 6](#).

The 6MWT is a non-encouraged test that measures the distance walked over 6 minutes. The 6MWT must be performed consistently across all patients and sites. Therefore, each test must be performed in strict accordance with the instructions and script provided in Section 19 of Appendix 1, which are based on American Thoracic Society (ATS) guidelines [ATS Statement 2002]. The appropriate language version will be applied for patients with a non-English informed consent.

Patients who require supplemental oxygen with exercise may use their prescribed oxygen level during 6MWTs. The oxygen level administered during Screening should be used during all subsequent tests. Titration of supplemental oxygen levels used during the 6MWT should only occur during the Screening Visit 6MWT via the site's standard oxygen titration/administration processes. If a patient's health status deteriorates during study participation and it is determined by a physician that the patient requires additional supplemental oxygen, the patient may continue study participation. However, the original supplemental oxygen level used during the Screening Visit 6MWT should continue to be used during all subsequent 6MWTs. In the opinion of the investigator, if a patient's health status deteriorates to the point that the patient can no longer safely conduct subsequent 6MWTs using the original supplemental oxygen set at the Screening Visit, then 6MWT should not be conducted.

At the completion of every 6MWT, the Borg dyspnea index will be recorded as well as results of pulse oximetry. Patients should not carry the pulse oximeter during the 6MWT; instead, pulse oximetry is to be collected at the beginning and end of the 6MWT using a headband, ear or finger probe. For patients with scleroderma in Cohorts 3a and 4a, a finger probe pulse oximeter should not be used.

Investigators or appropriate 6MWT administrators should not walk with the patient during the test.

9.10.24. Echocardiography

A screening echocardiogram (ECHO) will be completed and read locally to determine eligibility. Day 1 and all subsequent ECHOs will be sent to a core lab for reading. Pulmonary vascular resistance (PVR) and other hemodynamic measures will be estimated using a Doppler echocardiogram (ECHO) following a standardized protocol-specific procedure described in a separate manual. ECHOs will be performed at the time points indicated in [Table 3](#) or [Table 4](#) and [Table 5](#) or [Table 6](#). Other than during screening, echocardiography assessments will not be collected in patients enrolled in Cohort 3 and Cohort 4.

[REDACTED]

9.10.26. Pulmonary Function Testing

Pulmonary Function Testing that includes forced vital capacity (FVC), forced expiratory volume in 1 second (FEV1), FEV1/FVC ratio (FEV1%), peak expiratory flow (PEF), tidal volume (TV), and total lung capacity (TLC) will be performed at the time points indicated in [Table 3](#) or [Table 4](#) and [Table 5](#) or [Table 6](#).

[REDACTED]

[REDACTED]

[REDACTED]

[REDACTED]

[REDACTED]

[REDACTED]

[REDACTED]

[REDACTED]

[REDACTED]

9.10.32. Clinical Worsening

The Investigator or authorized designee will evaluate clinical worsening at the time points indicated in [Table 3](#) or [Table 4](#) and [Table 5](#) or [Table 6](#). If clinical worsening is suspected, further clinic evaluations may be required to document the protocol-defined (listed below) clinical worsening event (CWE).

- Death, or onset of treatment-emergent AE with a fatal outcome occurring less than or equal to 14 days after study treatment discontinuation;
- Heart-lung or lung transplant, or hospitalization for lung transplant;
- Atrial septostomy, or hospitalization for atrial septostomy;
- The patient requires the addition of any of the following medications:
 - Prostacyclin/prostacyclin analogue (intravenous, subcutaneous, oral, or inhaled) except for acute vasodilator testing during cardiac catheterization
 - Intravenous inotropes for right ventricular failure with appropriate documentation
 - Phosphodiesterase type-5 inhibitors
 - Endothelin receptor antagonist

- Riociguat
 - The combined occurrence of the events listed below. If a CWE is confirmed by these criteria, then an NT-pro BNP laboratory assessment is required on the day of the second 6MWT with the NT-Pro BNP sample obtained after 1 hour of rest:
 1. A decrease in 6MWT by at least 15% from Baseline, confirmed by two 6MWTs, on different days;
AND
 2. Increase (worsening) \geq 1 grade in WHO FC from Baseline;
AND
 3. Appearance of or worsening of signs/symptoms of right heart failure that did not respond to optimized oral diuretic therapy.

In case of clinical deterioration the Investigator must assess carefully if the deterioration of the patient's condition (e.g., worsening functional class) is related to the underlying pulmonary hypertension or can be explained by an alternative cause (e.g., transient infection, musculoskeletal disease, surgical or medical intervention other than pulmonary hypertension-related, exacerbation of a concomitant lung disease, lacking compliance of medication intake). Only persistent clinical deteriorations caused by the underlying pulmonary arterial hypertension will be considered a clinical worsening event.

Time to clinical worsening will be evaluated as the number of days between randomization and the occurrence of a predefined clinical worsening event.

Transient deteriorations of clinical status requiring hospitalization, treatable by, for example, short-time application of intravenous diuretics, positive inotropic agents or non-invasive ventilation and allowing patients discharge within 48 hours, are not considered to meet the criteria for a CWE. Patients should be discontinued only if any of the above criteria exceed 48 hours.

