6. If a patient is on chronic oxygen therapy, oxygen should be given at their standard rate or as directed by a physician or a protocol.

Reasons for immediately stopping a 6MWT include the following: (1) chest pain, (2) intolerable dyspnea, (3) leg cramps, (4) staggering, (5) diaphoresis, and (6) pale or ashen appearance.

Technicians must be trained to recognize these problems and the appropriate responses. If a test is stopped for any of these reasons, the patient should sit or lie supine as appropriate depending on the severity of the event and the technician's assessment of the severity of the event and the risk of syncope. The following should be obtained based on the judgment of the technician: BP, pulse rate, oxygen saturation, and a physician evaluation. Oxygen should be administered as appropriate.

TECHNICAL ASPECTS OF THE 6MWT**Location**

The 6MWT should be performed indoors, along a long, flat, straight, enclosed corridor with a hard surface that is seldom traveled. The walking course must be 15-30m in length. An approximate 49 to 98-ft hallway is, therefore, required. The length of the corridor should be marked every 3 meters. The turnaround points should be marked with a cone (such as an orange

traffic cone). A starting line, which marks the beginning and end of each lap, should be marked on the floor using brightly colored tape.

Rationale

A shorter corridor requires patients to take more time to reverse directions more often, reducing the 6MWT.

REQUIRED EQUIPMENT

1. Countdown timer (or stopwatch)
2. Mechanical lap counter
3. Two small cones to mark the turnaround points
4. A chair that can be easily moved along the walking course
5. Worksheets on a clipboard
6. A source of oxygen
7. Sphygmomanometer
8. Telephone
9. Automated electronic defibrillator

PATIENT PREPARATION

1. Comfortable clothing should be worn.
2. Appropriate shoes for walking should be worn. A notation should be made in the patient's source documentation of which shoes the patient wore for the first test. Prior to each clinic visit the patient should be called/reminded to ensure they wear this same pair of shoes.
3. Patients should use their usual walking aids during the test (cane, walker, etc.). NOTE – if a patient uses a walking aid for the first test this same aide should be used during all subsequent test whether needed or not.
4. The patient's usual medical regimen should be continued. The patient should continue to take doses of study drug prior to the test.

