If the patient stops walking during the test and needs a rest, say this: *"You can lean against the wall if you would like; then continue walking whenever you feel able."* **Do not stop the timer.** If the patient stops before the 6-minutes are up and refuses to continue (or you decide that they should not continue), wheel the chair over for the patient to sit on, discontinue the walk, and note on the worksheet the distance, the time stopped, and the reason for stopping prematurely.

When the timer is 15 seconds from completion, say this: *"In a moment I'm going to tell you to stop. When I do, just stop right where you are and I will come to you."*

When the timer rings (or buzzes), say this: *"Stop!"* Walk over to the patient. Consider taking the chair if they look exhausted. Mark the spot where they stopped by placing a bean bag or a piece of tape on the floor.

1. Post-test: Record the post-walk Borg dyspnea and fatigue levels and ask this: "What, if anything, kept you from walking farther?"
2. If using a pulse oximeter, measure SpO₂ and pulse rate from the oximeter and then remove the sensor.
3. Record the number of laps from the counter (or tick marks on the worksheet).
4. Record the additional distance covered (the number of meters in the final, partial lap) using the markers on the wall as distance guides.
5. Calculate the total distance walked, rounding to the nearest meter (i.e. 251.3 meters is 251 meters or 251.5 meters is 252 meters), and record it on the worksheet.
6. Congratulate the patient on good effort and offer a drink of water.

QUALITY ASSURANCE

Sources of Variability

There are many sources of 6MWT variability. The sources of variability caused by the test procedure itself should be controlled as much as possible. This is done by following the standards found in this document and by using a quality-assurance program.

Technician Training and Experience

Technicians who perform 6MWT should be trained using the standard protocol and then

supervised for several tests before performing them alone. They should also have completed cardiopulmonary resuscitation training.

Encouragement

Only standardized phrases for encouragement (as outlined above) must be used during the test.

Rationale

Encouragement significantly increases the distance walked. Reproducibility for tests with and without encouragement is similar. We have chosen every minute and standard phrases.

Supplemental Oxygen

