### 3.4.4 Efficacy Analysis

Analysis of the 6MWD will be performed using the mITT analysis set on all available data. Missing 6MWD data in Part 1 will be imputed using LOCF as described in Section 3.1.2. No imputation will be performed for missing 6MWD data in Part 2.

The CRF nominal study visits (i.e., Week 4, Week 8, Week 12, and Week 16) will be used for all 6MWT efficacy analyses. For subjects that prematurely discontinue treatment before Week 16 with a 6MWT recorded at the End of Treatment (EOT) assessment, that EOT 6MWD will be used in analysis for the nominal protocol visit most closely matching the subject's visit schedule. For all other efficacy analyses, the value closest to the target study day should be used (Section 3.7.2). In Part 1, LOCF will be applied to impute missing 6MWD values after analysis values are obtained taking into consideration the End of Treatment assessment, if applicable. For all other efficacy variables besides 6MWD, LOCF should not be used, and no imputation for missing data should be performed.

Analysis will pool all active doses within cohort for comparison with placebo in Part 1.

The analyses will be repeated for subgroups defined by PAH etiology in Part 1 (i.e., connective tissue disease vs non-connective tissue disease).

Given the exploratory nature of this study, sensitivity analysis may be performed in an ad hoc manner.

Plots will be generated to summarize 6MWT results by randomized treatment, pooling all placebo patients and all active patients into various subgroups:

- All PAH patients (Cohorts 1, 2, 3a, and 3b patients)
- All CTD-PAH patients (CTD-PAH patients in Cohorts 1, 2, and 3a)
- All Non-CTD PAH patients (Non-CTD PAH patients in Cohorts 1, 2, and 3b)
- All PH patients (Cohorts 4a, 4b, 4c, 4d)

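### The combined deterioration component of clinical worsening cannot be met when either confirmatory 6-minute walk is withheld as unsafe at the screening oxygen level, and no visible rule says how to score that patient.

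*Protocol*

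**What the plan says.** Protocol Section 9.10.32 (Clinical Worsening) lists several routes to an event. Death, transplant, septostomy and the addition of a listed medication need no walk test. The remaining route is a composite, introduced as "The combined occurrence of the events listed below", with its three items joined by AND. Item 1 is "A decrease in 6MWT by at least 15% from Baseline, confirmed by two 6MWTs, on different days". Item 2 is a rise of at least one grade in WHO class. Item 3 is new or worse right heart failure that has not responded to optimized oral diuretics. When this route is confirmed, an NT-proBNP sample is required on the day of the second walk. Time to clinical worsening is counted in days from randomization.

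Section 9.10.23 (6-Minute Walk Test) has a paragraph on supplemental oxygen that begins "Patients who require supplemental oxygen with exercise may use their prescribed oxygen level during 6MWTs". The oxygen level is fixed at screening for all later tests. If, in the investigator's opinion, the patient has deteriorated so far that he or she "can no longer safely conduct subsequent 6MWTs using the original supplemental oxygen set at the Screening Visit, then 6MWT should not be conducted". Appendix 1 repeats the instruction.

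The SAP, Section 3.4.4 (Efficacy Analysis), carries the last observation forward for 6MWD in Part 1. It then says: "For all other efficacy variables besides 6MWD, LOCF should not be used, and no imputation for missing data should be performed".

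**The concern.** Item 1 can be satisfied only by two tests that are carried out. The conduct rule foresees a patient who stays in follow-up but is too unwell to be tested at the screening oxygen level. Neither section refers to the other, and Section 9.10.32 says nothing about how item 1 is scored when a test is withheld.

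The absence of a walk is then caused by the deterioration that the component is meant to detect. A patient with moderate decline who can be walked twice can be recorded. A patient with a worse functional class and diuretic-refractory right heart failure who cannot be walked twice is not recorded by this route. Some of these patients would be treated as event-free, and others would receive a later event date through another route. The issue concerns time to clinical worsening. It does not concern the definition of the 6MWD primary efficacy endpoint.

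**Working it through.** The visible text gives no event rate, power or sample size for clinical worsening, so there is no stated figure to reproduce. The check sets the event definition beside the conduct and missing-data rules.

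**Inputs**
- Event definition, attribution rule and NT-proBNP timing: Protocol 9.10.32.
- Rule for not conducting the walk: Protocol 9.10.23, repeated in Appendix 1 under supplemental oxygen.
- Handling of walks stopped early: Protocol Appendix 1; SAP 3.4.4.1.
- Imputation: SAP 3.1.3 and 3.4.4.

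**Step 1: apply the definition case by case.** Assume items 2 and 3 are met and the decline is attributed to pulmonary hypertension.

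| Case | Item 1 | Component |
|---|---|---|
| Two walks conducted, both at least 15% below Baseline | met | event |
| Two walks started and stopped early, both distances at least 15% below Baseline | met | event |
| One walk at least 15% below Baseline, second withheld | not met | no event |
| Both walks withheld | not met | no event |

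The second row rests on Appendix 1, which tells staff to "discontinue the walk, and note on the worksheet the distance, the time stopped, and the reason for stopping prematurely". SAP 3.4.4.1 also keeps walks stopped for the listed safety reasons in the 6MWD analysis. The gap therefore concerns walks that are not conducted.

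**Step 2: look for a rule that rescues rows three and four.** Section 9.10.32 has no alternative for inability to walk and no waiver of the second test. The SAP bars imputation for efficacy variables other than 6MWD. Its carry-forward for 6MWD would repeat an earlier distance, so it would neither show the decline nor supply a second test on a different day.

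**Step 3: look for another route to an event.** Death, transplant, septostomy and addition of a listed drug remain open. Hospitalization counts only when it is for transplant or septostomy, and transient deteriorations with discharge within 48 hours are excluded. A patient in row three or four who later reaches one of the open routes is counted from that later date.

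**Step 4: bound the loss in general terms.** Let f be the fraction of patients with true deterioration of this kind for whom at least one of the two walks is withheld. The component can then record at most 1 − f of them. The documents do not give f. For illustration only, assumed values of f = 0.10 and f = 0.30 give 1 − 0.10 = 90% and 1 − 0.30 = 70%.

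**The case against.** The strongest defence is that few patients can fall through. To be missed altogether, a patient must be unwalkable at the screening oxygen level, have a worse functional class and have right heart failure refractory to oral diuretics. The same patient must also not die, have a transplant or septostomy, or be given any prostacyclin, intravenous inotrope, PDE-5 inhibitor, endothelin receptor antagonist or riociguat. Section 9.3.2 permits PAH drugs in WHO Group III and V patients, so the added-drug route is open in Cohort 4 too. This defence limits the size of the problem. It does not supply a scoring rule, and a later event by another route still shifts the event time.

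Four stronger readings are tempting and are not supported:

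- **That the protocol bars walking any patient who is too ill.** The instruction sits in the oxygen paragraph and concerns safety at the screening oxygen level, so it is narrower than a general ban.
- **That a walk must be completed to count.** The Appendix 1 list that opens "Reasons for immediately stopping a 6MWT include the following" deals with tests already under way, and those still give a distance.
- **That Cohort 4 is the most exposed because its patients may enter on up to 4 L/min of oxygen at rest.** Section 9.10.32 counts only persistent deterioration caused by the underlying pulmonary hypertension and names exacerbation of a concomitant lung disease as an alternative cause. A rising oxygen need in interstitial lung disease may not qualify even with a fallback.
- **That one missed event could reverse the apparent treatment effect.** With 4 × 24 = 96 Cohort 4 patients randomized 2:1, 32 receive placebo. An assumed 5–15% event rate gives 32 × 0.05 = 1.6 to 32 × 0.15 = 4.8 placebo events, so one event is 1/4.8 = 21% to 1/1.6 = 63% of them. That rate is assumed and covers all components. It is the same in both arms, and the missed event is taken from placebo only. The sum shows that small counts are fragile; it says nothing specific to this gap.

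**Conclusion.** The gap is real and should be closed. Following the protocol as written, a patient for whom either walk is withheld as unsafe at the screening oxygen level cannot meet the combined component, however clear the functional class and right heart failure evidence. This follows from the AND structure and does not depend on any assumed rate.

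Its size is unknown. The documents give neither an event rate for clinical worsening nor the proportion of deteriorating patients who could not be walked. They give no basis for saying which arm would be favoured; any bias would depend on whether severe, unwalkable deterioration differs by arm.

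Two limits apply. The loss is confined to this component, because the other routes remain. The exploratory endpoint list and most of the SAP's efficacy text after the primary analysis are redacted, so the endpoint's rank and any SAP rule for missing walks cannot be seen. The protocol's event definition is visible, and it has no fallback. The SAP calls the study exploratory and does not rest dose selection on a single endpoint, so this is an inexpensive repair to a predefined time-to-event measure.

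**What to change.** Reconcile Section 9.10.32 with Section 9.10.23 and Appendix 1 by changing how item 1 is scored. Who is walked or treated does not change.

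- Reword item 1 to require two assessments on different days. Each is met either by a 6MWD at least 15% below Baseline or by a documented inability to conduct the 6MWT because of deterioration attributed to the underlying pulmonary hypertension. Applying the choice to each assessment separately means that one low walk followed by one inability also qualifies.
- Keep items 2 and 3 and the existing attribution rule.
- Tie the NT-proBNP sample to the second assessment, since a second walk may not take place.
- Add an eCRF field for the reason whenever a 6MWT is not done, so that the component can be derived.
- State that the change governs endpoint scoring only, because Section 8.4 also lists clinical worsening among the reasons an investigator may discontinue a patient.

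The cost is one reworded item, one conforming edit and one eCRF field. The downside is that investigator judgement replaces a measured distance in a few patients. Items 2 and 3, the attribution rule and the need for two separate days limit that.
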